#### 13.9 Cancel

A patient is deemed a *cancel* if he/she is removed from the study for any reason before any study treatment is given. On-study material and the End of Active Treatment/Cancel Notification Form must be submitted. No further data submission is necessary.

**14.0 Body Fluid Biospecimens**

14.1 Summary Table of Research Blood Specimens to be Collected for this Protocol

| Correlative Study | Mandatory or Optional | Blood to Collect | Type Tube (color of tube top) | Volume to collect per tube (# of tubes to be collected) | Days to be Collected     | Storage /Shipping |
|-------------------|-----------------------|------------------|-------------------------------|---|--------------------------|-------------------|
| Biomarker study   | Mandatory             | Whole blood      | EDTA (purple top)             | 6 mL (3)  | Screen, C3D1, C5D1, C7D1 | Ambient           |
| Biomarker study   | Optional              | Whole blood      | EDTA (purple top)             | 6 mL (3)  | At disease progression   | Ambient           |

14.2 Collection and Processing

14.21 Whole blood samples will be collected via venipuncture for immune analysis (peripheral t-cell and other leukocyte phenotypes). Samples will be collected using 3 anticoagulant, spray-coated K2EDTA (plastic) purple-top tubes at the following timepoints:

- Screen
- Cycle 3 Day 1, Cycle 5 Day 1 and Cycle 7 Day 1 (prior to treatment)
- Optional at disease progression

14.22 Samples will be kept at ambient temperature prior to processing.

14.23 Samples will be processed and analyzed in [name] laboratory. [name] lab will pick up samples as soon as they are drawn for Rochester. For MCF and MCA ship ambient overnight so that samples arrive within 24 hours of being drawn.

14.3 Shipping and Handling

14.31 Kits *will not* be used for this study.

14.32 Samples collected in Rochester will be picked up by [REDACTED] lab.

14.33 Fresh (not frozen) samples collected at Florida or Arizona will be shipped overnight via Fed Express Monday through Thursday only (do not ship on a Friday or the day before a holiday) at ambient temperature to:

[REDACTED]  
 Mayo Clinic  
 [REDACTED]  
 Telephone: [REDACTED]  
 [REDACTED]

## 15.0 Drug Information

### 15.1 Anetumab Ravtansine (BAY 94-9343)

15.11 **Background:** Anetumab ravnansine is an antibody drug conjugate consisting of the monoclonal antibody BAY 86-1903 directed against the mesothelin antigen, a SPDB- (N-succinimidyl-4-(2-pyridyldithio) butanoate) linker and the tubulin polymerization inhibitor N-methyl-N- [4-mercapto-4-methyl-1-oxopentyl-L-alanine ester of maytansinol (DM4; BAY 1006640).

15.12 **Formulation:** Anetumab ravnansine is supplied as a freeze-dried product containing 60 mg anetumab ravnansine in a 30 mL injection vial. The following excipients are used to manufacture the medicinal drug product: histidine, hydrochloric acid, glycine, sucrose, polysorbate 80, and water for injection.

15.13 **Preparation and storage:** Vials containing the freeze dried product should be stored at 2-8°C. The lyophilisate is reconstituted with 11.9 mL sterile water for injection to produce a 5 mg/mL solution of active substance. The solution is further diluted in 0.9% sodium chloride or dextrose 5% solution (in a PVC or non-PVC infusion bag) to a concentration range of 0.1-3 mg/mL. A slight turbidity may occur during the dilution which does not affect the quality of the drug product. The reconstituted and diluted solutions are physically and chemically stable for 24 hours at room temperature and between 2-8°C. However, unless administered immediately, for microbiologic consideration, the reconstituted and diluted solutions should be stored between 2°C and 8°C and used within 6 hours. Exposure to bright light should be avoided.

15.14 **Administration:** Infuse over 60 minutes using an in-line 0.2 micron infusion filter.

15.15 **Pharmacokinetic information:** (Based on limited information from a small sample size). Maximum plasma concentrations of the anetumab ravnansine and total antibody were typically observed within 1 hour of end of infusion and, at the MTD of 6.5 mg/kg every three weeks, concentrations declined with geometric mean terminal phase t1/2 values of approximately 5 to 6 days.

15.16 **Potential Drug Interactions:** No data available.

15.17 **Known potential toxicities:** Corneal epithelial microcysts (15.8%), keratitis (28.9%), vision blurred (26.3%), diarrhea (52.6%), nausea (57.9%), vomiting (39.5%), infusion-related reaction (10.5%), asthenia (15.8%), fatigue (63.2%), ALT increased (18.4%), AST increased (28.9%), platelet count decreased (21.1%), decreased appetite (50.0%), peripheral neuropathy (21.1%)

15.18 **Drug procurement:** Bayer will provide drug to Biologics, Inc. Each participating site will order/monitor drug supply. Fax the Drug Order Request Form (found in the forms packet) to:

Outdated or remaining drug is to be destroyed on-site as per procedures in place at each institution.

15.19 **Nursing Guidelines:**

- 15.191 Infusion is over 60 minutes and requires an in line 0.2 micron infusion filter.
- 15.192 Given the early nature of this agent, not all side effects can be known at this time. Monitor patients closely and report any side effects to the study team.
- 15.193 Monitor LFT's , instruct patients to report abdominal pain and/or jaundice to study team.
- 15.194 Gastrointestinal side effects are common. Treat symptomatically and monitor for effectiveness.
- 15.195 Infusion related reaction can occur. Be sure to have emergency equipment available during infusion and monitor patient per protocol during infusion.
- 15.196 Eye related toxicity can occur and includes corneal epithelial microcysts, keratitis, and blurred vision. Instruct patients to report any visual changes, pain, tearing, etc to the study team immediately.
- 15.197 Fatigue is very common. Instruct patient in energy conserving lifestyle and monitor level of fatigue throughout treatment.
- 15.198 Peripheral neuropathy can be seen. Instruct patients to report any pain, numbness or tingling of the hand or feet to the study team immediately.

#### 15.2 **Atezolizumab** for IV Administration

- 15.21 **Background:** Atezolizumab is a human immunoglobulin (IgG1) monoclonal antibody that is produced in Chinese hamster ovary (CHO) cells. Atezolizumab targets programmed death-ligand 1 (PD-L1) on immune cells or tumor cells and prevents interaction with either programmed death-1 (PD-1) receptor or B7.1 (CD80), both of which function as inhibitory receptors expressed on T cells. Interference of the PD-L1:PD-1 and PD-L1:B7.1 interactions may enhance the magnitude and quality of the tumor-specific T-cell response through increased T-cell priming, expansion, and/or effector function. Atezolizumab shows anti-tumor activity in various nonclinical models and is being investigated as a potential therapy for cancer patients with locally advanced or metastatic malignancies.
- 15.22 **Formulation:** Atezolizumab is supplied in a single use vial as a colorless-to-slightly-yellow, sterile, preservative-free clear liquid solution intended for IV administration. The vial is designed to deliver 20 mL (1200 mg) of atezolizumab solution but may contain more than the stated volume to enable delivery of the entire 20 mL volume. The atezolizumab drug product is formulated as 60 mg/mL atezolizumab in 20 mM histidine acetate, 120 mM sucrose, 0.04% polysorbate 20, pH 5.8.
- 15.23 **Preparation and storage:** Atezolizumab must be refrigerated at 2°C–8°C (36°F–46°F) upon receipt until use. No preservative is used in atezolizumab drug product; therefore, the vial is intended for single use only. Discard any unused portion of drug left in a vial. Vial contents should not be frozen or shaken and should be protected from direct sunlight. Atezolizumab is administered using 0.9% sodium chloride 250 mL IV bags and infusion lines equipped with

0.2 micron in-line filters (filter membrane of polyethersulfone [PES]). Bags may be constructed of polyvinyl chloride (PVC) or polyolefin (PO).

- 15.24 **Administration:** The initial dose of atezolizumab will be delivered over 60 ( $\pm$  15) minutes. If the first infusion is tolerated without infusion-associated adverse effects, the second infusion may be delivered over 30 ( $\pm$  10) minutes. If the 30-minute infusion is well tolerated, all subsequent infusions may be delivered over 30 ( $\pm$  10) minutes.
- 15.25 **Pharmacokinetic information:**  
**Distribution:**  $V_{dss}$ : 6.9 L  
**Half-life elimination:** 27 days  
**Hepatic Impairment:** No clinically relevant effect with mild hepatic impairment. The effect of moderate or severe hepatic impairment on the pharmacokinetics of atezolizumab is unknown.  
**Renal Impairment:** No clinically relevant effect with renal impairment.
- 15.26 **Potential Drug Interactions:** No formal PK drug-drug interaction studies have been conducted with atezolizumab. The drug interaction potential of atezolizumab is unknown.
- 15.27 **Known potential toxicities:** Consult the package insert and investigator's brochure for the most current and complete information.  
**Common known potential toxicities, > 10%:**  
 Cardiovascular: Peripheral edema  
 Central nervous system: Fatigue  
 Dermatologic: Skin rash, pruritus  
 Endocrine & metabolic: Hyponatremia  
 Gastrointestinal: Decreased appetite, nausea, constipation, colitis, diarrhea, abdominal pain, vomiting  
 Genitourinary: Urinary tract infection, hematuria  
 Hematologic & oncologic: Lymphocytopenia  
 Infection: Infection  
 Neuromuscular & skeletal: Back pain, neck pain, arthralgia  
 Respiratory: Dyspnea, cough  
 Miscellaneous: Fever  
**Less common known potential toxicities, 1% - 10%:**  
 Cardiovascular: Venous thromboembolism  
 Central nervous system: Guillain-Barre syndrome, meningoencephalitis, myasthenia, myasthenia gravis, confusion  
 Endocrine & metabolic: Hyperglycemia, hypothyroidism, hypoalbuminemia, hyperthyroidism  
 Gastrointestinal: Increased serum amylase, increased serum lipase, pancreatitis, intestinal obstruction  
 Genitourinary: Urinary tract obstruction  
 Hematologic & oncologic: Anemia  
 Hepatic: Increased serum ALT/AST, hepatitis, increased serum alkaline phosphatase, serum bilirubin  
 Infection: Sepsis  
 Ophthalmic: Intraocular inflammation  
 Renal: Increased serum creatinine, acute renal failure

Respiratory: Pneumonitis, pneumonia

Miscellaneous: Infusion related reaction

**Rare known potential toxicities, <1% (Limited to important or life-threatening):**

Adrenocortical insufficiency, diabetes mellitus (with ketoacidosis), hypophysitis

15.28 **Drug procurement:** Atezolizumab will be from commercial sources.

15.29 **Nursing Guidelines:**

15.291 Anti PD-L1 side effects vary greatly from those of traditional chemotherapy and can vary in severity from mild to life threatening. Instruct patients to report any side effects to the study team immediately. Side effects may be immediate or delayed up to months after discontinuation of therapy. Most side effects are reversible with prompt intervention of corticosteroids

15.292 Diarrhea can be common and can be very severe, leading to colonic perforation. Instruct patients to report ANY increase in the number of stools and/or change in baseline, blood in the stool, abdominal pain to the study team immediately.

15.293 Rash/pruritis/dermatitis is seen. Patients should report any rash to the study team. Treat per section 8.0 and monitor for effectiveness.

15.294 Monitor LFT's closely as elevations in these levels could indicate early onset autoimmune hepatitis. Patients should also be instructed to report any jaundice, or right upper quadrant pain to the study team immediately.

15.295 Pneumonitis can be seen and may be mild (only seen on imaging) to severe. Patients should be instructed to report any SOB, dyspnea, cough, chest pain, etc. to the study team immediately. Patients reporting these symptoms should have a pulse ox checked and consider immediate imaging per the treating MD.

15.296 Endocrinopathies (including hypopituitarism, hypothyroidism, hypophysitis, and adrenal insufficiency) are a concern given the mechanism of action of this agent. Patients may present only with the vague sense of fatigue and "not feeling well". Additional symptoms may be that of nausea, sweating and decreased activity tolerance. Instruct patients to report these signs or symptoms immediately and obtain appropriate labs as ordered by MD.

15.297 Pancreatitis is possible with anti PD-L1 therapy based on mechanism of action. Instruct patients to report abdominal pain, nausea and vomiting to the study team.

15.298 Patients who are started on steroid therapy for any side effects of anti PD-L1 toxicity should be instructed to take the steroids as ordered, and not to discontinue abruptly as symptoms may return and be severe. Patients may be on steroid therapy for weeks. Instruct patients to report

any increase or change in side effects with any dosage decrease as patients may need a slower taper.

## 16.0 Statistical Considerations and Methodology

### 16.1 Overview

This is a non-randomized Phase I/II study designed to identify the recommended dose of anetumab ravtansine combined with atezolizumab and confirmed response rate in second line therapy of advanced NSCLC.

#### 16.11 Primary Endpoint

The primary endpoint of the phase I portion of this trial is to assess the maximum tolerated dose (MTD) of anetumab ravtansine combined with atezolizumab.

The primary endpoint of the phase 2 portion is the rate of confirmed response. A confirmed response is defined as a patient who has achieved a PR or CR on two consecutive evaluations at least 4 weeks apart. All patients meeting the eligibility criteria, who have signed a consent form and have begun treatment will be evaluable for response, unless they are determined to be a major violation. The first 6 months of treatment (i.e. 8 cycles) will be used to evaluate the primary endpoint of confirmed response.

#### 16.12 Sample Size

In the phase I portion, the study may involve as few as 6 patients (2 DLTs in Dose Level 1 and Dose Level -1) or as many as 12 patients (6 for each Dose Level). In addition, up to 37 patients will be treated at the recommended Phase II dose during the study (6 from phase I, 31 from phase II). Therefore, the maximum number of evaluable patients is 43 because the recommended Phase II dose will include 6 patients from the phase I portion. An additional 6 patients may be accrued to account for patients that need to be replaced bringing the maximum overall accrual to 49.

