**Study Design**

This is a non-randomized dose escalation Phase I study designed to determine the maximum tolerated dose (MTD) and dose-limiting toxicities of anetumab ravtansine (which will be dose-escalated) in combination with atezolizumab (administered at the standard fixed dose) in the treatment of advanced, treatment-refractory mesothelin expressing NSCLCs. This phase of the study uses a standard cohort 3+3 dose-escalation design. The patients will be treated with standard dose atezolizumab along with starting dose level 1 of anetumab ravtansine. Subsequent patient cohort(s) will be enrolled depending on the safety and tolerability of the initial cohort. If <33% patients treated at Dose Level 1 experience dose-limiting toxicity (DLT) by the end of first treatment cycle (21 days), then next cohort of 3 patients will be enrolled and treated at Dose Level 2. The MTD is defined as the maximum dose level at which  $\leq 1/6$  patients have DLTs. If DLT meets the stopping boundaries set by the above dose escalation algorithm at dose level 1 (for example, more than 1 out of 3 patients or more than 1 out of 6 patients), the next cohort of three patients will be entered at a dose level of -1. Further dose re-escalation will depend on the toxicity profile observed at dose level -1, and re-evaluation of the regimen by the study team may be done. A subsequent phase II study will be implemented once the recommended Phase 2 dose (RP2D) is ascertained. Anetumab ravtansine will be given IV once every 3 weeks and is subject to dose-escalation and atezolizumab is administered as a one-hour infusion every 3 weeks.

| Number of Patients | Cohort Level | Anetumab ravtansine (mg/kg) Q3W | Atezolizumab (mg) Q3W |
|--------------------|--------------|---------------------------------|-----------------------|
| 3-6                | -1           | 4.5                             | 1200 mg               |
| 3-6                | 1*           | 5.5                             | 1200 mg               |
| 3-6                | 2            | 6.5                             | 1200 mg               |

\*Starting dose  
 3+3 design; 3-6 pts/dose level. Total 6-12 patients in phase I.  
 Dose level I is starting dose level

|   |   |
|---|---|

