| 
Target Accrual and Study Duration
 | 
Duration:
 
Phase I: 3 months (maximum 6 months).
 
In the phase I portion, there will be 3-6 patients per dose level for a total of 6-12 patients.
 
Phase II stage 1: 6 months; stage II: 6 months.
 
Total duration: 15-18 months
 
In this part of the trial, 17 patients will be accrued (this will include the patients treated at the MTD from the phase I component). If 3 responses or less are observed in the first 17 patients, then the trial will be terminated and the treatment deemed not worthy of further study. If at least 4 responses are observed among these 17 patients, then an additional 20 patients will be accrued to the second stage. If 11 or more responses are observed at the end of the trial the treatment will be considered promising. This design yields at least 90% probability of a positive result if the true response rate is at least 40%. A maximum of 12 patients will be accrued to the phase I portion leading to a maximum of 49 patients for this study.
 |
|---|---|

|                                |  |
|--------------------------------|--|

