| Statistical Analysis | 
Sample Size Assumptions / Target Number of Valid Cases
 
A Simon two-stage design will be used in which a 20% response rate is considered not promising, a 40% response rate is considered promising, and the probabilities of a type I error (falsely accepting a nonpromising therapy) and type II error (falsely rejecting a promising therapy) are set at 0.10 and 0.10, respectively. In this scenario, the maximum trial size would be 37 patients. In the first stage of this design, 17 patients will be accrued (this will include the patients treated at the MTD from the phase I component). If 3 responses or less are observed in the first 17 patients, then the trial will be terminated and the treatment deemed not worthy of further study. If at least 4 responses are observed among these 17 patients, then an additional 20 patients will be accrued to the second stage. If 11 or more responses are observed at the end of the trial the treatment will be considered promising. This design yields at least 90% probability of a positive result if the true response rate is at least 40%. A maximum of 12 patients will be accrued to the phase I portion leading to a maximum of 49 patients for this study.
 
Interim Analyses
 
After 17 patients accrued on the phase II portion including patients treated at RP2D
 |
|-----------------------------|---|

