#### 16.21 MTD Definition

MTD is defined as the dose level below the lowest dose that induces dose-limiting toxicity (DLT) in at least one-third of patients (at least 2 of a maximum of 6 new patients). A total of 6 patients treated at the MTD will be sufficient to

identify common toxicities at the MTD. For instance, those toxicities with an incidence of at least 25% will be observed with a probability of at least 82% ( $1 - (1 - 0.25)^6$ ). Refer to Section 7.6 for definition of dose-limiting toxicity (DLT).

- 16.22 MTD Determination:  
Dose Escalation: The phase I portion of this study will utilize a standard cohort of three design. The first cohort of three patients will be treated at dose level 1. Decisions on when and how to dose escalate are described below.
- 16.23 The first cohort of three patients will be treated at the starting dose level 1.
- 16.24 Three patients will be treated at a given dose level combination and observed for at least 21 days from start of treatment to assess toxicity.
- 16.25 If DLT is not seen in any of the 3 patients, 3 new patients will be accrued and treated at the next higher dose level. If DLT is seen in 2 or 3 of 3 patients treated at a given dose level, then the next 3 patients will be treated at the next lower dose level, if only 3 patients were enrolled and treated at this lower level.
- 16.26 If DLT is seen in 1 of 3 patients treated at a given dose level, up to 3 additional will be enrolled and treated at the same dose level. If DLT is seen in at least one of these additional three patients ( $\geq 2$  of 6), the MTD will have been exceeded, and further accrual will cease to this cohort (see 16.113 for further details). If dose-limiting toxicity (DLT) is not seen in any of the three additional patients, 3 new patients will be accrued and treated at the next higher dose level.
- 16.27 After enrolling 6 patients on a specific dose level, if DLT is observed in at least 2 of 6 patients, then the MTD will have been exceeded and defined as the previous dose unless only 3 patients were treated at the lower dose level. In that case, 3 additional patients will be treated at this lower dose level such that a total of 6 patients are treated at the MTD to more fully assess the toxicities associated with the MTD.

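### The phase I maximum of 12 counts two of the three dose levels; the plan's own 3+3 rules can lead to as many as 18, so the 43 evaluable, the 6 replacement places and the 10- and 30-month maxima fail on some unlikely paths

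*Combined protocol and SAP*

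**What the plan says.** Section 16.12 gives the phase I range as "as few as 6 patients (2 DLTs in Dose Level 1 and Dose Level -1") to "as many as 12 patients (6 for each Dose Level"). It then counts 37 patients at the recommended dose (6 from phase I and 31 more), concludes that "the maximum number of evaluable patients is 43", and adds: "An additional 6 patients may be accrued to account for patients that need to be replaced". That makes 49 overall.

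The Protocol Synopsis repeats the range ("Total 6-12 patients in phase I" and "there will be 3-6 patients per dose level for a total of 6-12 patients"). It reaches 49 differently: "A maximum of 12 patients will be accrued to the phase I portion leading to a maximum of 49 patients for this study".

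The dose tables in the synopsis and in 7.11 list three levels (-1, 1, 2) with 3 to 6 patients each, starting at level 1. The rules that set the count are:

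- 16.25: after 0/3 DLTs, escalate with only 3 treated. After 2 or 3 of 3, the next 3 go to the level below if it has only 3.
- 16.26 and 16.27: after 1/3, expand to 6. If at least 2 of 6 have a DLT, the level is exceeded, and a lower level holding only 3 is filled to 6.
- 16.28: if level 1 meets the boundary (more than 1 of 3 or of 6), the next three patients enter level -1.
- 16.621: the lower level is filled to at most 6.

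Section 16.21 adds "A total of 6 patients treated at the MTD will be sufficient" to identify common toxicities. Section 16.13 allows 2.5 months per cohort of three, a phase I maximum of 10 months for 4 cohorts, and an overall maximum of 30 months.

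**The concern.** One sentence in 16.12 uses level -1 to obtain its minimum but leaves one level out of its maximum. Nothing in 16.2 closes level -1 once level 2 has been visited, and no rule stops phase I at 12. On some permitted paths the stated maximum and the dose-finding rules therefore cannot both be followed.

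If 12 is a hard cap, those paths stop with level -1 unopened or holding only 3 patients. The only text for that situation is the discretionary re-evaluation by the study team in 16.28. If the rules are followed instead, the 43, the replacement margin and the duration maxima are wrong. The accrual ceiling and timetable are commitments, and they would come under strain exactly when toxicity is higher than expected.

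**Working it through.** **Reproducing the plan's figures.** Two levels × 6 = 12. Then 12 + 37 − 6 shared = 43, and 43 + 6 = 49. For time, 4 × 2.5 = 10 months and 10 + 16 + 4 = 30 months. All agree, but only with two levels. The synopsis route is 12 + 37 = 49, which counts the six shared patients twice and leaves no replacement places.

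**Paths above 12.** These follow 16.25 to 16.28 and 16.621 in full cohorts of three, with 6 patients at the MTD and no re-escalation after level -1 (16.28 leaves that open). The possible totals are 6, 9, 12, 15 and 18. Three cohort sequences exceed 12:

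- 1, 2, 1, −1, −1: 15 patients; level -1 is the MTD, or there is none.
- 1, 2, 2, 1, −1: 15 patients; level -1 fails in its first three, so there is no MTD and no phase II.
- 1, 2, 2, 1, −1, −1: 18 patients; level -1 is the MTD, or there is none.

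**Consequences if level -1 is the MTD and phase II runs to 37** (31 further patients):

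- 15 in phase I: 15 + 31 = 46 evaluable; 49 − 46 = 3 places left; 5 × 2.5 = 12.5 months of phase I.
- 18 in phase I: 18 + 31 = 49 evaluable; 49 − 49 = 0 places left; 6 × 2.5 = 15 months of phase I.

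Where level -1 also fails, only the 12 and the 10 months are wrong.

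**How likely.** The documents give no DLT rate for the combination, so the rates are assumed and patients are treated as independent. The model's single-level escalation probability, (1−p)³ + 3p(1−p)²(1−p)³, gives 0.906, 0.709, 0.494, 0.309 and 0.172 at p = 10% to 50%. This matches the table in 16.29b.

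| Assumed DLT rate at −1/1/2 | P(N > 12) | P(15, MTD = −1) | P(18, MTD = −1) |
|---|---|---|---|
| 5/10/15% | 0.5% | 0.1% | 0.3% |
| 5/10/20% | 0.7% | 0.2% | 0.5% |
| 10/20/35% | 3.6% | 1.3% | 1.9% |
| 10/25/50% | 5.8% | 2.9% | 2.3% |
| 15/30/50% | 6.4% | 2.9% | 2.2% |
| 25/40/60% | 6.5% | 2.6% | 1.3% |
| 5/36/60% | 7.4% | 4.9% | 2.3% |
| 5/36/42% | 6.1% | 2.9% | 3.1% |

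These are chosen scenarios, not limits. As a cross-check, every path above 12 needs 0/3 and then at least 2 of 3 at level 1. Under this model P(N > 12) therefore cannot exceed (1−p)³(3p² − 2p³), where p is the level 1 rate. At p = 0.36 this is 0.2621 × 0.2955 = 0.077, about its peak.

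The evaluable total reaches 46 or 49 only if the second stage also opens. P(at least 4 of 17) is 0.45 at a 20% response rate and 0.95 at 40%.

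**Two-stage rule.** Continuing with at least 4 of 17 and succeeding with at least 11 of 37 gives a type I error of 0.095 at 20% and power of 0.903 at 40%. Neither depends on the phase I total.

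**The case against.** **The 18-patient path needs full expansion cohorts.** Section 7.2 allows stopping at 2 of 4 subjects, and 16.26 speaks of up to 3 additional patients. If expansion stops at the second DLT, totals between 12 and 18 other than 15 also occur, and exactly 18 with level -1 as MTD falls to about 0.1% to 0.3% in the first six scenarios. This stands as a limit on the size of the problem. It does not rescue the 12, because P(N > 12) hardly changes (for example 5.8% to 5.7% at 10/25/50%).

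**The durations are approximate.** Section 16.13 words them so, but its 10-month maximum is tied explicitly to 4 cohorts, and the rules allow 6.

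**Stronger readings that the documents do not support:**

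- That the 25-month overall minimum is impossible and must be 27.5. This assumes the top level must be expanded to 6. After 0/3 at level 1 and 0/3 at level 2, sections 16.25 to 16.27 contain no rule to expand level 2. Read literally, that is a 2-cohort path: 5 + 16 + 4 = 25. The 6 phase I patients in 16.12 and the synopsis MTD criterion of at most 1 in 6 point the other way, so this is an ambiguity and not a proven error.
- That 35 months is the correct overall maximum. The sum 15 + 16 + 4 = 35 carries forward a 4-month assessment time that sits badly with the 6-month response window in 16.11.
- That the ceiling of 49 is breached and must rise to 55. Before replacements, 49 evaluable fits within 49, and 16.12 says only that replacements may be accrued. It does not guarantee six places on every path.

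**Conclusion.** The point holds as a minor arithmetic inconsistency. The phase I maximum under the written rules is 18, not 12. The maximum evaluable is 49, not 43, but only if phase I takes 18 patients, level -1 becomes the MTD and phase II is completed; on the 15-patient path it is 46. The replacement margin then falls from 6 to 0 or 3. The phase I maximum is 15 months, not 10, and the 30-month overall maximum built on it fails.

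The probability of exceeding 12 is about 0.5% to 7.4% across the scenarios. This rests on assumed DLT rates, independent patients, 6 patients at the MTD and no re-escalation after level -1. Decision rules, type I error and power are untouched.

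**What to change.** Choose one of two routes.

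1. Restate the phase I maximum as 18 and the maximum evaluable as 49 in 16.12, and the phase I range in the synopsis to match. State that, when level -1 is the MTD and phase II is completed, the ceiling of 49 leaves 3 replacement places after 15 phase I patients and none after 18. In 16.13, give phase I as up to 15 months (6 × 2.5), and recalculate the overall maximum once the 4-month assessment time has been reconciled with the 6-month window in 16.11.
2. If 12 is meant as a cap, say so and reconcile it with 16.25 to 16.28 and 16.621, including what happens when the cap is reached before those rules are complete.

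Under either route, derive 49 in the synopsis as 16.12 does: remove the shared six, then add replacements (43 + 6 as the text now stands). The cost is a few sentences in 16.12, 16.13 and the synopsis (route 2 also touches the escalation rules), with no change to the ceiling or the two-stage rules.
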